NOTE: A unique data element includes any unique features that alone are not identifiable but that could be used to identify an individual within the context of other information, such as any type of code (such as diagnosis or procedural), rank of general or admiral, gender, or race. Triangulation means using different data elements that when combined can be used to identify an individual, such as including the above lists of unique data elements in a data set. Determining whether an individual is identifiable through triangulation requires consideration of all data elements in combination. Within the military, the use of rank and/or diagnosis code, procedural codes, or any other code that changes on a predictable basis, increases the possibility of identification. Small cell size means that there is only a small number of eligible individuals that satisfy the category description. Department of Defense Manual 6025.13, Medical Quality Assurance and Clinical Quality Management in the Military Health System MHS, provides that the threshold for de-identifying data within the MHS requires a cell size of three, but also states that the de-identification standards must meet the DoD implementation of the HIPAA Privacy Rule. Centers for Medicare and Medicaid also gives quidance on small cell size stating that no data cell less than 11 may be published or displayed. However, the Office for Civil Rights' OCR, which is the official regulatory office for the HIPAA Privacy Rule, provides that OCR does not designate a universal value for small cell size in accordance with the de-identification standard; instead, the cell size should be set at a level that is appropriate to mitigate risk of identification by the anticipated recipient of the data set. This means that a cell size of 3 or 11 may not meet the HIPAA Privacy Rule requirements if the cell size level does not appropriately mitigate risk of identification by the anticipated recipient of the data set.

Note: If dates are altered as a means of de-identifying the data, diagnosis and procedural codes need to be rolled-up or collapsed. If dates are provided "as time between events," the roll-up is not necessary.

Yes, the DHA data will become identifiable	е
■ No, the DHA data will not become identifi	abl

10.12 Do you believe it is possible for the MHS data to become identifiable because of triangulation, a small cell size, or any unique data element(s)?

Triangulation means using different data elements that are not themselves identifiable but that when combined can be used to identify an individual. For example, triangulation would use rank and race together to determine the identity of an individual with a particular health condition.

Small cell size means that there is only a small number of eligible individuals that satisfy the category description. Guidance for acceptable cell size is available from the Centers for Medicare and Medicaid Services. For example, the rank category of four star generals with a particular diagnosis may be less than 30, so the rank category may need to be expanded to include lower ranks.

A unique data element includes any unique features that are not explicitly enumerated in the categories of data in rows 1-20 of the table above (in Section 10.10), but that could be used to identify an individual. Unique data elements include characteristics that are not themselves identifying, such as the rank of general or admiral, or a race or gender, but within the context of other information could be identifiable.

 Yes, I believe there is a reasonable possibility the MHS data will become identifiable No, I believe there is no reasonable possibility the MHS data will become identifiable 	
10.13 Have you completed and uploaded an appropriate HIPAA document (i.e. HIPAA Authorization of HIPAA Authorization is being requested)?	orization will
 Yes No N/A If yes, please check which one. HIPAA Authorization HIPAA Waiver (Full or Partial) Other (please provide copies when uploading Other Study Documents) 	

10.14 Managing Data (Data Management and/or Sharing Plan) and/or Human Biological Specimens for this Study:

Include in this section the plan for acquiring data (both electronic and hard copy), access during the study, data/specimen storage and length of time stored, shipment/transmission, and the plan for storage and final disposition at the conclusion of the study. Describe any data agreements in place for accessing data within and/or outside of your institution (e.g., Data Sharing Agreement, Data Use Agreement, Business Agreements, etc.)

Data Capture Methods:

The local study team will collect study data directly from the study participant (including in person, via mail or email, or over the phone), from their attending provider(s), clinical evaluations or, where applicable, from the participant's medical record (i.e., relevant medical and treatment history and relevant clinical notes) and record it on study Case Report Forms (CRFs) (see Appendices A-F, T-U).

The completed CRFs will serve as source documents for this study. Other source documents include relevant clinical notes, imaging, and/or test results which, if applicable, will be redacted and stored in the participant's research file.

Participants may also enter their coded data directly into REDCap using a personalized survey link (no log-in required). In these cases, the completed REDCap questionnaire(s) will be printed and added to the participant's research record as a source document.

Electronic Data Entry:

Following each research visit, a local study team member will review any completed paper CRFs for accuracy and completeness and then enter the collected non-personally identifiable data from the paper CRFs into REDCap, an encrypted, access controlled, password protected electronic data capture and management system housed on a Department of Defense (DoD) server and maintained by the Uniformed Services University Information Technology (USU IT).

Please see Appendix R for additional information on REDCap.

Ultrasound images will be uploaded to Teleray, more information is outlined below.

Data Storage & Access:

With the exception of the Informed Consent Form, HIPAA Authorization, Intake CRF, and electronic Master List (see Appendix G), all research data (both paper and electronic) will be identified using a unique study ID only, and not by the participant's name, date of birth, DoD ID, or other protected identifier.

Paper research forms and source documents will be stored in a locked cabinet inside of a locked room within the Podiatry Clinic.

Ultrasound images will be uploaded to Teleray. Teleray ensures that all accounts stored in Microsoft Azure's self-healing network with advance security protocols enabled and is only located in the USA Secure Connection: The sessions established are secure (with secured tokens

that are regenerated). Random AES keys are generated by clients at the beginning of the media connection and, to increase security, additional keys are generated periodically throughout the session. Teleray employs Transport Layer Security (TLS) to encrypt video data. The core protocols used are Secure Real-time Transport Protocol (SRTP) for media traffic encryption and Datagram Transport Layer Security (DTLS)-SRTP for key negotiation, both of which are defined by the Internet Engineering Task Force (IETF). The endpoints use Advanced Encryption Standard (AES) cipher with 256-bit keys to encrypt audio and video, and Hash-based Message Authentication Code- Secure Hash Algorithm 1 (HMAC-SHA1) to verify data integrity. No PHI/PII will be entered into Teleray. Access to the coded data uploaded to Teleray will be controlled and managed by the local research team.

The coded electronic research data for this study will be stored in REDCap, an encrypted, access controlled, password protected electronic data capture and management system housed on a Department of Defense (DoD) server and maintained by the Uniformed Services University Information Technology (USU IT). No PHI/PII will be entered into REDCap.

This coded electronic research data will be accessible by authorized staff from Musculoskeletal Injury Rehabilitation Research for Operational Readiness (MIRROR) which is based out of the Department of Physical Medicine & Rehabilitation (PM&R) at the Uniformed Services University (USU) and is serving as the data coordinating center for this research study. Access to the electronic coded research data will be governed strictly on an individual-by-individual basis within REDCap. Individual data access as well as privileges will be clearly delegated, audited, and monitored by MIRROR/USU. Staff from MIRROR/USU will not have access to the paper research records or any identifiable research data.

The local study team will maintain a separate electronic master list which matches unique study IDs with participant identifying information. The electronic master list will be stored separately from the coded electronic research data in a secure, password protected document on a computer and network that requires CAC access and will only be accessible by local research staff.

All research data and forms (both paper and electronic) will only be accessible by authorized study staff, authorized staff from MIRROR/USU (coded data entered into REDCap and Teleray only, as described above), the IRB of record, the local research office (if applicable), and applicable governmental agencies as part of their duties and in accordance with federal law. These duties include making sure that research participants are protected.

There will be appropriate data sharing agreements in place.

Informed Consent Forms and HIPAA Authorizations will be maintained for a period of 6 years following study closure and then securely shredded. Paper research forms will be maintained for a period of 5 years following study closure and then securely shredded. The master list connecting unique study ID to participant identifiers will be destroyed as soon as all data collection is completed and analyzed, and no later than one year following study closure. The electronic coded research data will be maintained indefinitely as described below in protocol section 10.15.

Is this a data repository?		
O Yes O No		
If Yes, provide name of the Repository.		
N/A		
Who will have access to the Repository?		
N/A		
What data type will be stored in the Repository?		
□ PHI		
LDS		
☐ De-identified Data		

10.15 Managing Data (Data Management and/or Sharing Plan) and/or Human Biological Specimens for Future Research:

If the study involves collecting, storing, or banking human specimens, data, or documents (either by the Investigator or through an established repository) for FUTURE research, address. How the specimens/data will be used, where and how data/specimens will be stored (including shipping procedures, storage plan, etc.), whether and how consent will be obtained, procedures that will fulfill subjects' request as stated in the consent, whether subjects may withdraw their data/specimens from storage, whether and how subjects may be recontacted for future research and given the option to decline, whether there will be genetic testing on the specimens, who will have access to the data/specimens, and the linkage, the length of time that data/specimens will be stored and conditions under which data/specimens will be destroyed.

Long Term Data Storage & Access:

The de-identified electronic dataset will be maintained by MIRROR/USU and the study team indefinitely or as long as it is practicable to maintain.

The de-identified data uploaded to Teleray will be maintained by the local research team indefinitely, or as long as it is practical to maintain, and while funding is allotted for this service.

De-identified electronic research data will be securely transmitted from local study teams to the MIRROR /USU via REDCap, Teleray, or the DoD SAFE application (or other comparable safe data sharing system implemented by the local site and/or the US Army/DHA). REDCap utilizes Secure Sockets Layer (SSL) in addition to other safeguards on its web server to maintain secure communication with end-users (see Appendix R). DoD SAFE uses a TLS (Transport Layer Security) protocol when files are uploaded and downloaded. TeleRay employs Transport Layer Security (TLS) to encrypt video data. The core protocols used are SRTP for media traffic encryption and DTLS-SRTP for key negotiation, both of which are defined by the IETF. The endpoints use AES cipher with 256-bit keys to encrypt audio and video, and HMAC-SHA1 to verify data integrity.

Once received, the electronic de-identified research data will be stored within an encrypted, access controlled, password protected electronic data capture and management system housed on a Department of Defense (DoD)-compliant server.

Access to the de-identified research data will be governed strictly on an individual-by-individual basis within the secure electronic data capture and management system. Individual data access as well as privileges will be clearly delegated, audited, and monitored by MIRROR/USU.

Any future research using retained data will require a research protocol to be approved by an Institutional Review Board or other authorized official responsible for protecting human subjects of research.

Consent for Future Use:

The Informed Consent Form for this research study states that de-identified research data will be shared with MIRROR/USU and maintained indefinitely for possible use in future research. By consenting to participate in this research study, participants agree to allow us to maintain their de-identified research data indefinitely for possible use in future research.

Participants will not be given the option to opt out of us retaining their de-identified research data indefinitely for possible future use. The consent form states, "If you do not want your deidentified data collected as part of this research study to be kept for use in future research studies, you should not sign this consent form."

We are also requesting to store identifiable data for possible use in future research. Participants will be given the option to opt-in or opt-out for the possible use of their identifiable data in future research.

Data Withdrawal from Storage:

Participants may request to have their data withdrawn at any time before their personal identifiers have been removed. Once their data has been de-identified, it will be impossible for the researchers to locate their specific study data.

Is this a	data repository?	

If Yes, provide the name of the Repository

USU OCIO REDCap

Who will have access to the Repository?			
MIRROR core team members, study investigators and study team members, as appropriate			
What data type will be stored in the Repository?			
□ PHI			
LDS			
✓ De-identified Data			
11.0			
Statistical/Data Analysis Plan			
11.1 Statistical Considerations:			
List the statistical methods to be used to address the primary and secondary objectives, specific aims, and/or research hypotheses. Explain how missing data and outliers will be handled in the analysis. The analysis plan should be consistent with the study objectives. Include any subgroup analyses (e.g., gender or age group). Specify statistical methods and variables for each analysis. Describe how confounding variables will be controlled in the data analysis. Descriptive statistics for each variable will be reported as central tendencies in terms of location (e.g., mean, median) and scale (e.g., variance, interquartile interval). Inferential analyses will use the Mann-Whitney U test (a non-parametric analogue of Student's t-test) for simple comparisons and regression analysis with outcome-appropriate distribution families and link functions for multivariable comparisons. The FAAM sports subscale will be standardized by the multiplicative inverse of the patient-level maximum possible score. The primary outcome will be computed as the patient-level, six-week change in standardized FAAM sports subscale. Sensitivity analyses will be conducted using regression to control for patient-level demographics. Hypothesis tests will be two-tailed and statistical significance will be considered at the putative threshold (alpha=0.05). Effect sizes will be compared to a minimum clinically important difference.			
11.2 Sample Size:			
Assuming approximately 20% attrition, we are requesting to enroll up to 100 participants (approx. 50 per arm).			
11.3 Total number of subjects requested (including records and specimens):			
100			
11.4 If you are recruiting by study arm, please identify the arms of the study and how many subjects will be enrolled in each arm			
Up to 100 participants will be randomized to one of two study arms (PBMT+UC or Sham-PBMT+UC) in a simple, random fashion, with approximately 50 participants in each arm.			

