All participants, regardless of study arm assignment, will be asked to complete the UC Protocol (Appendix H) which consist of a daily regimen of stretching and cryotherapy that includes 3-5 minutes of stretching upon waking, then approximately 3-5 minutes of stretching and 3-5 minutes of cryotherapy throughout the day, for the duration of 6 weeks (instructions and participant handout will be provided, Appendix I).

Participants will receive PBMT or sham-PBMT with the PBM device (Appendix J, Figure 1) over the course of three consecutive weeks (three treatments per week). PBM treatments will take

approximately 5-10 minutes to administer at each session. Specific treatment parameters will be based on measurements of calf, ankle, and foot using pre-calculated treatment tables; participants will receive 10 J/cm2, 25W output power, and the length of the treatment will be dependent on treatment area (size).

Photobiomodulation Therapy (PBMT):

PBMT will be administered by a trained member of the study team using the LightForce® XPi therapy laser, provided by LiteCure, LLC/DJO Global (New Castle, DE). The LightForce® XPi therapy laser is an FDA cleared device for the treatment of pain. The trained team members will use the Smart Hand Piece technology, which achieves effective treatments and improves dosing accuracy by assessing the operator's speed and providing real-time visual (red – amber – green light) and sensory feedback (Appendix J, Figure 2). The Smart Hand Piece is calibrated to shutoff when moving too slowly, and warn the operator when moving too fast by vibrating. The therapy is delivered through a flexible optical fiber threaded through the hand piece, which contains a rolling sapphire massage ball. The PBM therapy will be administered by rolling the massage ball over the plantar surface of the foot and dorsal aspect of the calf in contact with the participants' skin.

Sham-Photobiomodulation Therapy (Sham-PBMT):

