In addition to their 3x weekly for 3 weeks PBM or Sham-PBM treatments, participants will report to the study team in person approximately 3 weeks (+/- 3 days) and 6 weeks (+/- 3 days) after the start of their PBM or Sham-PBM treatment to complete the follow-up questionnaires (Appendix E), turn in their Pain Diary (Appendix F), and undergo ultrasound imaging to measure changes in plantar fascia thickness at 3-weeks and 6-weeks (see below).

Long-term follow-up questionnaires may be captured remotely (e.g., entered directly into REDCap using a personalized coded link with no log-in required, verbally over the phone with a study team member, etc.), or in-person (using Appendix U Long-Term Follow-Up Data Collection CRF) at approximately 3 months (+/- 10 days) post-start of PBM treatment. For Sham-PBMT participants who cross-over, their 3-month follow-up will be timed from the first day of their active PBM treatment, not their Sham-PBM treatment. Reminder phone calls and emails will be sent to participants at the phone and email address provided to the study team before the 3-month follow-up time point.

Participants will be evaluated for adverse events at each follow-up time point and any complications will be documented.

Study participation ends after the 3-month follow-up research activities are completed. Participants initially randomized to the PBMT group will participate in the study for approximately 3 months. Participants initially assigned to the Sham-PBMT group who choose to crossover and receive active PBMT post-unblinding will be in the study for approximately 4.5 months total. If the participant is a biological female of child-bearing age and/or capacity, they will be required to complete another hCG urine pregnancy test at this time. Results must be negative (i.e., indicating not pregnant) to be eligible to continue with PBM treatment. If the results are positive (i.e., indicating pregnant), the participant will be deemed ineligible by formal screening criteria, and they will be ineligible to receive the elective study treatment.

Ultrasound Measurement:

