Defense and Veterans Pain Rating Scale (DVPRS) 72. This 5-item scale integrates a numeric pain rating scale Veterans Pain with visual facial cues and word descriptors as well as 4 supplemental questions on pain interference. Construct validity using component factor analysis revealed one item group (factor loadings > .78 and > .81) for outpatient and inpatient participants, respectively, with high internal consistency (.87-.90). (51, 52)

Aim 1: Primary outcome measure for pain; DVPRS collected at baseline, daily days 2-43 (during and post treatment), 3 months.

The daily Diary will include the DVPRS, and space to document any medications taken and activity completed during each 24-hour period to attempt to explain potential variation. (Appendices D, E, & F)

Ultrasound Measurement above.

(Plantar fascial thickness) Ultrasound measurement as described in section 10.1

Aim 2: Primary outcome measure for effect of PBMT on plantar fascial thickness (change in thickness); collected at baseline, 3 weeks, and 6 weeks

10.3 At any point in the study, will you request, use, or access health information in any form, including verbal, hard copy and electronic?

Yes
No

10.4 Review the definitions below and respond to the following two questions. If you are not sure of the answers, email [contact] for assistance. The Military Health System (MHS) is defined as all DoD health plans and DoD health care providers that are organized under the management authority of, or in the case of covered individual providers, assigned to or employed by, the Defense Health Agency (DHA), the Army, the Navy, or the Air Force MHS workforce members are employees, volunteers, trainees, and other persons whose conduct, in the performance of work for the MHS, is under the direct control of the MHS, whether or not they are paid by the MHS. MHS business associates are persons or entities that provide a service to the MHS and require protected health information (PHI) to provide the service.

	Yes, I am an MHS workforce memberNo, I am not an MHS workforce member	
	Are you an MHS business associate?	
	Yes, I am an MHS business associateNo, I am not an MHS business associate	
	10.5 Have you consulted with an MHS data expert to determine the data elements required	for your study?

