14.0 Risks and Benefits

14.1

Risks of Harm:

Identify all research-related risks of harm to which the subject will be exposed for each research procedure or intervention as a result of participation in this study. Consider the risks of breach of confidentiality, psychological, legal, social, and economic risks as well as physical risks. Do not describe risks from standard care procedures; only describe risks from procedures done for research purposes

Research Procedure Name: Photobiomodulation (PBM) Therapy Research Procedure Description: Light therapy for Plantar Fasciitis (PF)

The potential risks directly associated with study-specific activities and procedures are minimal. PBM treatment is used by a variety of healthcare practitioners for painful clinical conditions. Potential research-related risks include damage to eye structures and uncomfortable skin heating, which are both very rare.

Additionally, any time information is collected for a study, there is a small risk of breach of confidentiality.

14.2

Measures to Minimize Risks of Harm (Precautions, safeguards):

For each research procedure or intervention, describe all measures to minimize and/or eliminate risk of harms to subjects and study personnel

Protective eyewear will be worn by all participants and study team members during treatment sessions to avoid damaging their eyes.

All applicable study team members will complete a battery of training modules and hands-on training sessions to ensure safe operation of the PBMT device, and compliance with local laser safety requirements and American National Standards Institute (ANSI) standards Z136.1 (Safe Use of Lasers) and Z136.3 (Safe Use Lasers in Health Care). See Appendix K for the laser operator training plan.

A member of the research team will serve as a clinical laser safety officer (CLSO) to establish and manage the study-specific laser safety program. The designee will work with the MAMC Laser Safety Officer (LSO) and participate in the MAMC Laser Safety Committee (LSC) meetings quarterly to receive proper training. Along with the LSO and CLSO, the PI will ensure that the treatment space meets all regulatory requirements for utilization of a treatment laser, including appropriate signage and use of laser blocking screens to absorb any potential scatter/refraction of light outside of the treatment area.

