In the rare occurrence that participants experience uncomfortable warmth over the treatment area, the treatment will be modified or stopped.

In order to protect participant confidentiality, research data will be identified using a unique study ID only, and not by participant name, date of birth, DoD ID, or other similar identifier. All available measures allowed by law will be taken by research staff to protect participant confidentiality. See protocol section 14.3 for additional information

All participants will be evaluated for adverse events at each follow-up visit. All adverse events, regardless of severity, will be reported to the Principal Investigator. Adverse events will also be reported according to the guidelines stated in Protocol Section 16.

14.3 Confidentiality Protections (for research records, data and/or specimens):

Describe in detail the plan to maintain confidentiality of the research data, specimens, and records throughout the study and at its conclusion (e.g., destruction, long term storage, or banking). Explain the plan for securing the data (e.g., use of passwords, encryption, secure servers, firewalls, and other appropriate methods). If data will be shared electronically with other team members/collaborators outside the institution, describe the method of transmission and safeguards to maintain confidentiality. Explain whether this study may collect information that State or Federal law requires to be reported to other officials or ethically requires action, e. g., child or spouse abuse

Upon consenting for the study, participants will be assigned a unique study ID. With the exception of the Informed Consent Form, HIPAA Authorization, and electronic Master List, all research data (both paper and electronic) will be identified using this unique study ID only, and not by the participant's name, date of birth, DoD ID, or other protected identifier.

Paper research forms and source documents will be stored in a locked cabinet inside of a locked room within the Podiatry Clinic, accessible only by local research staff designated and authorized by the Principal Investigator. The paper Intake CRF which records participant contact information, Informed Consent Forms and HIPAA Authorizations will be stored separately from the coded paper research forms in a locked cabinet inside of a locked room within the Podiatry Clinic, accessible only by authorized local research staff.

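### The only scheduled adverse-event evaluations described are at the follow-ups, the first at day 18-24, by which time most or all of the nine laser sessions have been given

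*Combined protocol and SAP*

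**What the plan says.** Two sections set the timing of adverse-event evaluation, and they agree. Section 10.1, under Follow-Up Data Collection, states "Participants will be evaluated for adverse events at each follow-up time point and any complications will be documented". Section 14.2 states "All participants will be evaluated for adverse events at each follow-up visit".

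Section 10.1 places the in-person follow-ups "approximately 3 weeks (+/- 3 days) and 6 weeks (+/- 3 days) after the start of their PBM or Sham-PBM treatment" and the last one "at approximately 3 months (+/- 10 days) post-start of PBM treatment". The last need not be in person: "Long-term follow-up questionnaires may be captured remotely". The same section presents these follow-ups as additional to the treatment visits, which number three a week for three weeks. Its descriptions of the active and sham sessions mention no adverse-event question or record.

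Section 14.1 names the physical risks: "Potential research-related risks include damage to eye structures and uncomfortable skin heating, which are both very rare". Section 10.2 describes the daily diary as holding the DVPRS and "space to document any medications taken and activity completed during each 24-hour period to attempt to explain potential variation".

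Other text also bears on safety:
- Section 14.2 has treatment modified or stopped if warmth becomes uncomfortable, and sends all adverse events to the principal investigator.
- Section 15.1 has on-site physicians monitor participants and has adverse-event data tracked.
- Section 16.1 puts expected and unrelated events on an Adverse Event Tracking Log.

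**The concern.** Skin heating is tied to the laser session: it arises during a session or soon after. A planned question that first comes around week 3 is poorly placed to pick it up. A participant whose skin was red for a day after session 1 would first be asked, by plan, 18 to 24 days later. Until then the record depends on the participant volunteering the event or on the operator choosing to note it.

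That second route matters in a sham-controlled trial. Under Section 10.1 the operator leaves the standby button and finger switch inactive for sham sessions, and so knows the allocation. The sham ball is warmed too, so mild warmth is possible in both arms. Without a fixed question, what is noted could differ by arm for reasons unrelated to the laser.

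Section 15.1 gives early identification of increased risk as a reason for tracking adverse events. A first scheduled evaluation after most of the exposure does little for that aim.

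**Working it through.** The plan states no event rate or similar figure on this point, so there is none to reproduce. The check is of the calendar.

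**Inputs (Section 10.1).** Three sessions a week for three weeks; follow-ups at 3 weeks ± 3 days and 6 weeks ± 3 days, counted from the start of treatment. The first session is taken as day 0.

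**Sessions.** 3 × 3 = 9.

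**Windows.** The 3-week visit is 21 ± 3 = day 18 to 24. The 6-week visit is 42 ± 3 = day 39 to 45.

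**Delay for an event after session 1.** 18 − 0 = 18 days at the earliest and 24 − 0 = 24 days at the latest.

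**Sessions before the window opens.** The documents name no treatment weekdays, so four weekly patterns are assumed, each begun on any of its three weekdays, with no missed visits. Cells show the number of sessions before day 18, with the day of the ninth session in brackets.

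| Assumed weekdays | Begin on first weekday listed | Begin on second | Begin on third |
|---|---|---|---|
| Mon, Wed, Fri | 8 (day 18) | 8 (day 19) | 8 (day 19) |
| Tue, Thu, Fri | 9 (day 17) | 8 (day 19) | 7 (day 20) |
| Mon, Tue, Wed | 9 (day 16) | 8 (day 20) | 7 (day 20) |
| Mon, Tue, Thu | 9 (day 17) | 8 (day 20) | 7 (day 19) |

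For example, Mon-Wed-Fri begun on a Wednesday gives days 0, 2, 5, 7, 9, 12, 14, 16 and 19, with eight of these before day 18.

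Across the twelve cases, 7 to 9 sessions precede day 18. The ninth falls on day 16 to 20, so all nine precede day 21. A visit early in the window can come before the last one or two sessions, and rescheduled sessions could shift the count further.

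**Crossover.** Section 10.1 has participants who cross over repeat the original procedures apart from screening and baseline collection. The same interval therefore recurs in their active course.

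**What fills the interval.** Reporting to the principal investigator and entry on the log begin once an event is known; neither brings one to light. Physician monitoring does not rest on a known event, but it has no stated schedule, question or form. The in-session response covers warmth felt during treatment, not effects appearing between sessions.

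**The case against.** The strongest reply is that participants are far from unobserved. A trained team member delivers every session with the ball on the treated skin. All adverse events of any severity go to the principal investigator, and physicians monitor progress. Everyone wears protective eyewear, the handpiece shuts off when moved too slowly, the device is used within its labelling, the pilot treatment was well tolerated, and the study is classed as minimal risk. All of this stands, and it keeps the point modest. It does not supply a scheduled question during the treatment weeks.

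A reader might infer more than the documents support:
- *That adverse events are assessed only at follow-up.* Sections 14.2, 15.1 and 16.1 provide other routes. Only scheduled evaluation is confined to the follow-ups.
- *That a modified or stopped session goes unrecorded.* Uncomfortable heating is a named risk. As an adverse event it must reach the principal investigator and, if expected, the log.
- *That events will be under-counted.* No event rate or recall figure is given, so this is a possibility, not a finding. It fits transient skin effects better than eye damage, which need not be brief. A pain flare would show in the daily DVPRS, although the diary is handed in at follow-up.
- *That a planned active-versus-sham safety comparison is compromised.* The aims in Section 9.3 and the analyses in Sections 11.1 and 11.6 contain no safety analysis.
- *That the 24-hour reporting clocks are delayed for the named risks.* Section 16.1 applies them to specified unexpected events and unanticipated problems. Expected events go to continuing review or study closure.

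One limit remains. The case report forms, diary form and adherence log are cited as appendices but are not in the text reviewed. A session form with an adverse-event item cannot be ruled out.

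**Conclusion.** The point holds in a limited form. Followed as written, the plan first schedules an adverse-event evaluation at day 18-24. With no missed visits and under the assumed weekdays, that is after 7 to 9 sessions when the window opens and after all nine at the target day. The crossover course has the same gap. No standard question at treatment visits is described, so transient effects may be captured incompletely, or unevenly by arm. The extent cannot be estimated from the documents. The efficacy analyses are unaffected. This is an inexpensive improvement to safety data collection that the sponsor should make, not a fault that puts the trial in doubt.

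**What to change.** In Sections 10.1 and 14.2, extend adverse-event evaluation to every treatment visit as well as every follow-up, in both arms and in the crossover course. Use one short question with fixed wording, covering the current session and the time since the last one. Record the answer with date and session number, and record in the same way any session modified or stopped under Section 14.2. Enter positive answers on the existing Adverse Event Tracking Log. Keep the three follow-up evaluations.

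If a session form already does this, cite it and bring the two sections into line with it.

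The cost is a change of wording, a few lines on a form and about a minute per session at visits where trained staff are already present. More minor events will be logged in both arms. This concerns data collection only; no dose, stopping rule or other clinical rule is proposed.
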